5.1.1.3.4 Multiple Comparisons Procedure for Primary and Secondary Endpoints

The overall familywise error rate (FWER) will be controlled at $\alpha = 0.05$ for the set of primary and secondary endpoint comparisons between each dose level of ubrogepant vs. placebo both for the US analyses and for the EU analyses.

A graphical approach by Bretz et al (2009) will be used to control the overall type I error rate for multiple comparisons across the ubrogepant doses and the primary and secondary efficacy endpoints. For the US analyses, the coprimary efficacy endpoints will serve as the gatekeepers of the secondary endpoints. [REDACTED]

[figure not shown]
[REDACTED]. The secondary endpoints will be tested in the same order as they appear in the list of secondary endpoints, except for the 2 migraine-associated symptoms, photophobia and phonophobia, which will be treated at the same level to allow the recycling of weights among the 2 symptom endpoints. Recycling of weights between the 2 doses from nausea to pain freedom is also allowed.

[figure not shown]
Using graphical approach with the weighted Bonferroni-based closed test procedure, the endpoints are represented by circles with associated weights inside the circle. The weight is the fraction of α , representing local significance levels. The fraction in the rectangle, associated with a line connecting two circles, indicates the fraction of the local significance level of the circle at the beginning of the line which is added to the local significance level of the circle at the end of the line, if the null hypothesis at the beginning circle is rejected.

Figure 5-9 Multiple Comparisons Procedure for the US**Table 5-16 Multiple Comparisons Procedure Definitions for the US**

Circle	Alternative Hypothesis	Objective	Weight	Local Significance Level
25mgP1	Primary Efficacy Endpoint 1 for 25 mg ubrogepant is significantly different from placebo	PO1	1/2	$\alpha^*(1/2) = \alpha/2$
25mgP2	Primary Efficacy Endpoint 2 for 25 mg ubrogepant is significantly different from placebo	PO1	0	$\alpha^*0 = 0$
25mgS3	Secondary Efficacy Endpoint 1 for 25 mg ubrogepant is significantly different from placebo	PO1	0	$\alpha^*0 = 0$
25mgS1	Secondary Efficacy Endpoint 2 for 25 mg ubrogepant is significantly different from placebo	PO1	0	$\alpha^*0 = 0$
25mgS2	Secondary Efficacy Endpoint 3 for 25 mg ubrogepant is significantly different from placebo	PO1	0	$\alpha^*0 = 0$
25mgS4a	Secondary Efficacy Endpoint 4a for 25 mg ubrogepant is significantly different from placebo	PO1	0	$\alpha^*0 = 0$
25mgS4b	Secondary Efficacy Endpoint 4b for 25 mg ubrogepant is significantly different from placebo	PO1	0	$\alpha^*0 = 0$
25mgS4c	Secondary Efficacy Endpoint 4c for 25 mg ubrogepant is significantly different from placebo	PO1	0	$\alpha^*0 = 0$
50mgP1	Primary Efficacy Endpoint 1 for 50 mg ubrogepant is significantly different from placebo	PO1	1/2	$\alpha^*(1/2) = \alpha/2$
50mgP2	Primary Efficacy Endpoint 2 for 50 mg ubrogepant is significantly different from placebo	PO1	0	$\alpha^*0 = 0$
50mgS3	Secondary Efficacy Endpoint 1 for 50 mg ubrogepant is significantly different from placebo	PO1	0	$\alpha^*0 = 0$

50mgS1	Secondary Efficacy Endpoint 2 for 50 mg ubrogepant is significantly different from placebo	PO1	0	$\alpha^*0 = 0$
50mgS2	Secondary Efficacy Endpoint 3 for 50 mg ubrogepant is significantly different from placebo	PO1	0	$\alpha^*0 = 0$
50mgS4a	Secondary Efficacy Endpoint 4a for 50 mg ubrogepant is significantly different from placebo	PO1	0	$\alpha^*0 = 0$
50mgS4b	Secondary Efficacy Endpoint 4b for 50 mg ubrogepant is significantly different from placebo	PO1	0	$\alpha^*0 = 0$
50mS4c	Secondary Efficacy Endpoint 4c for 50 mg ubrogepant is significantly different from placebo	PO1	0	$\alpha^*0 = 0$

5.1.1.4.1 Study Treatment Exposure and Compliance

Study treatment exposure will be summarized and listed for the Safety Population.

The summary of treatment exposure will include the number and percentage of participants who took the initial dose only, the number and percentage of participants who took both the initial dose and the optional second dose, and the number and percentage of participants who took the PK dose for each treatment group.

The listing of treatment exposure will indicate whether the participant took the optional second dose and [REDACTED] in addition to the first dose.

Treatment compliance to the first dose of study medication will not be calculated as participants are only to take 1 tablet.

[REDACTED] [REDACTED]
[REDACTED]

[REDACTED] [REDACTED]

[REDACTED]	[REDACTED]
[REDACTED]	[REDACTED]
[REDACTED]	[REDACTED]
[REDACTED]	[REDACTED]

[REDACTED]

[REDACTED]

[REDACTED]	[REDACTED]	[REDACTED]	[REDACTED]
[REDACTED]	[REDACTED]	[REDACTED]	[REDACTED]
[REDACTED]	[REDACTED]	[REDACTED]	[REDACTED]
[REDACTED]	[REDACTED]	[REDACTED]	[REDACTED]
[REDACTED]	[REDACTED]	[REDACTED]	[REDACTED]
[REDACTED]	[REDACTED]	[REDACTED]	[REDACTED]
[REDACTED]	[REDACTED]	[REDACTED]	[REDACTED]
[REDACTED]	[REDACTED]	[REDACTED]	[REDACTED]

Parameter	Description	Timing	Methodology
[REDACTED]	[REDACTED]	[REDACTED]	[REDACTED]

[REDACTED]

[REDACTED]

[REDACTED]

[REDACTED]

[REDACTED]

[REDACTED]	[REDACTED]	[REDACTED]	[REDACTED]
[REDACTED]	[REDACTED]	[REDACTED]	[REDACTED]
[REDACTED]	[REDACTED]	[REDACTED]	[REDACTED]
[REDACTED]	[REDACTED]	[REDACTED]	[REDACTED]
[REDACTED]	[REDACTED]	[REDACTED]	[REDACTED]
[REDACTED]	[REDACTED]	[REDACTED]	[REDACTED]
[REDACTED]	[REDACTED]	[REDACTED]	[REDACTED]

[REDACTED]

[REDACTED]

[REDACTED]

[REDACTED]	[REDACTED]	[REDACTED]	[REDACTED]
[REDACTED]	[REDACTED]	[REDACTED]	[REDACTED]

[REDACTED]

[REDACTED]

[REDACTED]

[REDACTED]	[REDACTED]	[REDACTED]	[REDACTED]
[REDACTED]	[REDACTED]	[REDACTED]	[REDACTED]

[REDACTED]

[REDACTED]

[REDACTED]

[REDACTED]	[REDACTED]	[REDACTED]	[REDACTED]
[REDACTED]	[REDACTED]	[REDACTED]	[REDACTED]
[REDACTED]	[REDACTED]	[REDACTED]	[REDACTED]
[REDACTED]	[REDACTED]	[REDACTED]	[REDACTED]

[REDACTED]

[REDACTED]

[REDACTED]

[REDACTED]

[REDACTED]	[REDACTED]	[REDACTED]	[REDACTED]
------------	------------	------------	------------

[REDACTED]

[REDACTED]

[REDACTED]

[REDACTED]	[REDACTED]	[REDACTED]	[REDACTED]
[REDACTED]	[REDACTED]	[REDACTED]	[REDACTED]
[REDACTED]	[REDACTED]	[REDACTED]	[REDACTED]
[REDACTED]	[REDACTED]	[REDACTED]	[REDACTED]

[REDACTED]

5.1.1.5 Subgroup Analyses

The following subgroup analyses will be conducted by historical triptan response. PF and absence of the most bothersome migraine-associated symptom at 2 hours after initial dose will be analyzed using similar models as the primary endpoints with the additional treatment group by historical triptan response interaction. Time to PF and absence of the most bothersome migraine-associated symptom within 2 hours after the initial dose will be analyzed by historical triptan response separately.

- *PF at 2 hours after initial dose*
- *Absence of the most bothersome migraine-associated symptom at 2 hours after initial dose (US only)*
- *Time to PF within 48 hours after the initial dose*
- *Time to absence of the most bothersome migraine-associated symptom within 48 hours after the initial dose (US only)*

A pooled analysis among triptan insufficient responders across ubrogepant pivotal studies will be conducted to demonstrate statistically significant efficacy in the triptan insufficient responders' population.

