12.6 Protocol Amendment 3 Summary

Title: A Phase 3, Multicenter, Randomized, Double-blind, Placebo-controlled Single Attack Study to Evaluate the Efficacy, Safety, and Tolerability of Oral Ubrogapant in the Acute Treatment of Migraine

Protocol UBR-MD-02 Amendment 3

Date of Amendment: 19 May 2017

Amendment Summary

This summary includes changes made to Protocol UBR-MD-02 Amendment 2, (04 Nov 2016). This protocol was amended to: 1) increase sample size from 450 to 550 patients per arm; 2) revise statistical methods to include an additional categorical term to the logistic regression analysis for the primary efficacy variable of absence of the most bothersome symptom at 2 hours after the initial dose; 3) revise statistical methods to include an additional categorical term to the logistic regression analysis for the secondary efficacy endpoints on migraine-associated symptoms; 4) reorder the secondary endpoints, [REDACTED] and 6) remove the 35% triptan insufficient responder requirement.

Following is a summary of content-oriented changes that were made to each section of the protocol, and a brief rationale for these changes. Minor editorial and document formatting revisions have not been summarized.

Section	Revision	Rationale
Title Page	Replaced Emergency Telephone Number and Allergan Medical Monitor Contact Information with instructions to refer to Study Contacts Sheet.	Administrative update
Protocol Summary, Section 3 Study Design, Section 4.1 Number of Patients	Increased number of patients to be randomized to approximately 1650 (550 patients per treatment arm).	Sample size re-estimate based on updated assumptions

Section	Revision	Rationale
Section 5.5 Method for Assignment to Treatment Groups/Randomization/ [REDACTED]	Removed requirement that at least 35% of [REDACTED]	[REDACTED]
Section 7.2.2 Secondary Efficacy Variable	[REDACTED]	[REDACTED]

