4.1 Study Design Summary

Structure: Multicenter, randomized, double-blind, placebo-controlled, parallel-group, single attack study; randomization to placebo, ubrogepant 25 mg, or ubrogepant 50 mg.

Duration: The study includes a screening period of up to 14 days prior to randomization, a 60-day period in which to treat a single migraine attack, and a 4-week follow-up period.

Study Treatment Groups: Ubrogapant 25 mg, ubrogepant 50 mg

Controls: Ubrogapant placebo

Dosage/Dose Regimen: Study participants will have up to 60 days to treat a single qualifying migraine attack of moderate or severe headache pain intensity at home. Participants have the option to take a second dose of investigational product (IP) or rescue medication if the participant has either a nonresponding migraine or a migraine recurrence. Participants who are randomized to ubrogepant arms will be randomly assigned at the Randomization Visit (Visit 2) to active treatment or placebo (1:1) for the blinded optional second dose. Participants randomized to the placebo arm will receive placebo for their blinded optional second dose.

Randomization: [REDACTED] Participants will be randomized (1:1:1) to 1 of the following 3 treatment groups: placebo, ubrogepant 25 mg, or ubrogepant 50 mg. [REDACTED]

Number of Participants: Approximately 1650 participants will be randomized (550 per treatment arm).

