5.1.1.1.3 Statistical Methodology

The methodologies defined below apply as specified to individual endpoints defined in this SAP. All statistical tests will be 2-sided hypothesis tests performed at the 5% level of significance for

main effects. All confidence intervals will be 2-sided 95% confidence intervals, unless stated otherwise.

Table 5-2 Statistical Methodology

Methodology	Description
M1 Categorical counts	
 • Number of participants in individual categories 
 ○ Participants with ≥ 1 qualifying event counted once per individual category
M2 Categorical descriptives	
 • Number and percentage of participants in individual categories 
 ○ Participants with ≥ 1 qualifying event counted once per individual category • N1 if proportion denominator \neq number of participants in the population (standard percentage denominator) 
 ○ N1 = participants with non-missing baseline value
[REDACTED]	[REDACTED]
[REDACTED]	[REDACTED]
M5 Continuous descriptives	
 • N1, mean, standard deviation (SD), median, minimum, maximum • N1 = participants with non-missing value
M6 CFB descriptives	
 • Continuous descriptives for baseline, postbaseline, and change from baseline (CFB) values • N1 = participants with non-missing values at both baseline and the specified postbaseline analysis visit
[REDACTED]	[REDACTED]
M8 Responder	
 • Categorical descriptives using proportions for responders and nonresponders 
 ○ Nonresponders include: 
 ▪ Participants who do not meet responder criteria • N1 = all participants unless otherwise specified
[REDACTED]	[REDACTED]
M10 Logistic regression model	
 • Measures the relationship between the binary categorical dependent variable (responder or nonresponder) and independent variables 
 ○ Independent variables for initial dose: 
 ▪ treatment group (placebo, ubrogepant 25 mg, ubrogepant 50 mg) ▪ historical triptan response (triptan responder, triptan insufficient responder, or triptan naïve) ▪ use of medication for migraine prevention (yes, no) ▪ baseline headache severity (moderate or severe)

Methodology	Description

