	
Note: Historical triptan response and use of medication for migraine prevention are stratification factors for the study.
 
For the analysis of individual migraine-associated symptoms, baseline presence/absence of the symptom will be included as an additional covariate in the logistic regression model.
 
[REDACTED]
 
[REDACTED]
 
 ○ If the logistic regression model fails to converge due to complete or quasi-complete separation, Firth’s penalized likelihood method (Firth, 1993) will be used. The profile penalized likelihood approach (Heinze and Schemper, 2002) will be used to make valid inference. • Formal test of efficacy hypothesis comparing 2 active treatments vs Placebo conducted using pairwise contrasts based on odds ratios and their 95% confidence intervals of the odds ratio 
 ○ Calculate two-sided p-values
[REDACTED]	[REDACTED]

CFB = change from baseline; ANCOVA = analysis of covariance.

Raw and derived data listings will be provided, and will be fully defined in the table, figure, and data listing specification document.

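### SAP 5.1.1.5 analyses the time-to-event endpoints separately within each triptan-response group and, as specified, includes no test or estimate of whether the effect differs between groups, although it plans an interaction term for the 2-hour binary versions

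*SAP*

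**What the plan says.** SAP 5.1.1.5 plans subgroup analyses by historical triptan response and uses two methods.

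- **Binary endpoints at 2 hours** (pain freedom, absence of the most bothersome symptom): "similar models as the primary endpoints with the additional treatment group by historical triptan response interaction".
- **Time to each of the same two outcomes:** "within 2 hours after the initial dose will be analyzed by historical triptan response separately". No interaction term, heterogeneity test or rule for reading the group results together is stated.

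The bulleted list under those sentences gives a different window for the time-to-event endpoints, for example "Time to PF within 48 hours after the initial dose". The SAP amendment summary, section 1.5.10, carries the same wording.

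The subgroup factor has three levels: "historical triptan response (triptan responder, triptan insufficient responder, or triptan naïve"). SAP Table 5-2 also notes: "Historical triptan response and use of medication for migraine prevention are stratification factors for the study". Treatment comparisons within a triptan group are therefore properly randomised. The readable text gives no expected share for each group, and Protocol Amendment 3 lists among its changes to "remove the 35% triptan insufficient responder requirement".

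**The concern.** With two doses and three groups, separate analyses yield six dose-versus-placebo results per endpoint. None of them addresses whether the effect differs between groups. A reader is then likely to compare which groups reach significance, and that is not a test of effect modification. A group can miss significance because it is small, and the effect may be the same everywhere.

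This matters most for the insufficient responders. The same section plans a pooled analysis across the pivotal studies to demonstrate efficacy in them, so their results here will be looked at closely. A miss due to size alone could be read as lack of effect, while the binary analysis of the same outcome in the same trial shows no interaction.

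**Working it through.** **Inputs.** Protocol Table 4 gives 2-hour rates (placebo, ubrogepant) of 10% and 24% for pain freedom and 26.7% and 37.7% for the most bothersome symptom. SAP 4.1 gives the size: "Approximately 1650 participants will be randomized (550 per treatment arm"). Tests are two-sided at 5%; no other level is stated for subgroups, so nominal 5% is used.

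**The plan's own figures.** There is none for these subgroup analyses. The nearest is Table 4's whole-population power: above 99% for pain freedom and 88% for the most bothersome symptom. A pooled two-proportion test with 550 per arm at two-sided 0.025 (the starting level per dose in SAP Table 5-16) gives above 99.9% and 95.3%. The 88% is reached at about 420 per arm (420/550 = 76%). The sample-size text is redacted, so the 88% can be neither confirmed nor called wrong. It does show that the evaluable number may be well below 550. I use 413 (75% of 550) to 550 per arm.

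**Step 1: hazard ratios implied at 2 hours**, HR = ln(1 − p1)/ln(1 − p0).
- Pain freedom: ln(0.76)/ln(0.90) = 2.60; ln HR = 0.957.
- Most bothersome symptom: ln(0.623)/ln(0.733) = 1.52; ln HR = 0.421.

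**Step 2: power in one group** with share s of n per arm, one dose versus placebo, same HR in every group. Events are d0 = n·s·p0, d1 = n·s·p1 and d = d0 + d1. Two standard approximations:
- A: Φ(ln HR × √(d/4) − 1.96)
- B: Φ(ln HR / √(1/d0 + 1/d1) − 1.96)

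**Step 3: chance of a mixed pattern** (some groups significant, others not) = 1 − Π(power) − Π(1 − power).

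Worked case: most bothersome symptom, 550 per arm, equal thirds. d = 550 × 1/3 × 0.644 = 118.1. Power A = Φ(0.421 × √29.5 − 1.96) = Φ(0.33) = 0.628. Mixed = 1 − 0.628³ − 0.372³ = 0.701.

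| Endpoint | n per arm | Shares | Power by group (A) | Mixed (A) | Mixed (B) |
|---|---|---|---|---|---|
| Most bothersome symptom | 550 | thirds | 0.628 each | 0.701 | 0.710 |
| | 550 | 50/20/30 | 0.800, 0.425, 0.583 | 0.754 | 0.760 |
| | 413 | thirds | 0.509 each | 0.750 | 0.750 |
| | 413 | 50/20/30 | 0.680, 0.336, 0.468 | 0.780 | 0.779 |
| Pain freedom | 550 | thirds | 0.966 each | 0.100 | 0.193 |
| | 550 | 50/20/30 | 0.996, 0.833, 0.948 | 0.213 | 0.320 |
| | 413 | thirds | 0.906 each | 0.256 | 0.388 |
| | 413 | 50/20/30 | 0.980, 0.718, 0.874 | 0.384 | 0.505 |

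The two formulas agree for the most bothersome symptom and differ for pain freedom, where events are few and unbalanced. If one group holds only 10% (60/10/30, formula A, 420–550 per arm), the chance of a mixed pattern is 83–84% and 49–62% respectively.

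**Step 4: the alternative.** A 2-df heterogeneity test on the three independent log hazard ratios for one dose, simulated under a constant effect, rejected in 4.9–5.1% of runs. Its power is limited. With the effect absent in insufficient responders only, 468–550 per arm, and equal thirds or 40/25/35, it is about 46–62% for pain freedom and 24–33% for the most bothersome symptom.

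**Step 5: the 48-hour window.** The documents give no 48-hour rates. Assuming HR 1.15–1.5 and 50–90% of patients with an event, the chance of a mixed pattern runs from 12% to 76%. That range is too wide to serve as an estimate.

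**The case against.** The strongest points on the other side are these.

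- **The method is partly unreadable.** The time-to-event row of SAP Table 5-2 and the endpoint rows of Table 5-14 are blacked out. Cox models, log-rank tests or Kaplan-Meier displays alone would all fit the sentence. This stands as a limit on what can be said about p-values. It does not undo the word that the section itself uses for how the groups are handled.
- **Effect modification is already tested.** Both coprimary outcomes at 2 hours are analysed "with the additional treatment group by historical triptan response interaction". This stands, and it rules out the reading that the trial does not examine whether the effect depends on triptan history. The gap is confined to the time-to-event versions, including any time course to 48 hours.
- **The separate results do not preclude a test.** A reader might infer that separate analyses cannot show a difference. The groups are disjoint, so if hazard ratios and standard errors are reported, a 2-df test can be built from them. The plan just does not specify one.
- **Separate estimates suit a within-group aim.** The only aim the section states is efficacy in insufficient responders, through the pooled analysis. That these analyses are meant to assess effect modification is an inference. The pooling also partly answers the worry about small size for that group.
- **The harm depends on a reading rule the SAP does not contain.** This is correct. The mixed-pattern figures apply only if the results are read as significant or not.

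**Conclusion.** The point holds as a gap in specification: the time-to-event subgroup analyses carry no stated test or estimate of a between-group difference, while the sentence before them plans one for the binary versions.

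If the results are read by significance, a constant effect gives a mixed pattern with probability about 70–78% for the most bothersome symptom and about 10–50% for pain freedom, against 5% with an interaction test. This rests on Table 4's 2-hour rates, proportional hazards, 413 to 550 evaluable per arm, a smallest group of at least 20%, nominal 5%, and one dose versus placebo. The group shares and the evaluable number are assumptions.

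A reader might infer that misleading patterns are likely for both endpoints. The figures support that for the most bothersome symptom. For pain freedom the answer depends on the evaluable number, the shares and the approximation used. Neither range carries over to 48 hours.

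The matter is minor. These analyses lie outside the multiplicity procedure in SAP 5.1.1.3.4 and do not bear on the primary conclusion. The conflict between the 2-hour and 48-hour windows is a separate inconsistency that can be seen without any calculation.

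**What to change.** Replace the sentence on separate analysis in SAP 5.1.1.5 with one proportional-hazards model per endpoint:

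- baseline hazard stratified by historical triptan response;
- treatment group, the other covariates and a treatment-by-triptan-response interaction;
- the interaction test named in advance: 2 df for each dose versus placebo, or 4 df across both doses (2 × 2);
- group hazard ratios with 95% confidence intervals reported next to the interaction p-value, and the whole labelled exploratory because interaction power is limited. A non-significant interaction should not be read as proof of a common effect;
- any by-group displays retained.

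In the same edit, state one time window so that the sentence and the bullets agree.

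The cost is a sentence or two of SAP text and minor programming, with no new data. The downside is that the other covariate effects are assumed common across the triptan groups, which separate fits would not require.

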5.1.1.6 Interim Analyses

Not applicable.

[Redacted text block]

[Redacted text block]

[Redacted]	[Redacted]	[Redacted]	[Redacted]
[Redacted]	[Redacted]	[Redacted]	[Redacted]
[Redacted]	[Redacted]	[Redacted]	[Redacted]
[Redacted]	[Redacted]	[Redacted]	[Redacted]

5.2 Changes in the Conduct of the Study or Planned Analyses

Prior to database lock, there were no changes in study conduct or planned analyses from what was described in the [protocol](#) and detailed in the SAP.

5.2.1 Changes in the Conduct of the Study

Not applicable.

5.2.2 Changes to Analyses Prior to Database Lock

Not applicable.

6. Data Handling and Analysis Conventions

6.1 Study Treatment Conventions

6.1.1 Analysis Days

Treatment day is defined as follows:

Table 6-1 Analysis Day Definitions

Term	Description
Treatment Day	Relative to treatment start date If analysis date \geq treatment start date: 
 • Day = analysis date – treatment start date + 1 
 ○ Day 1 = treatment start date If analysis date $<$ treatment start date: 
 • Day = analysis date – treatment start date 
 ○ Day -1 = day before treatment start date ○ There is no Day 0

